#### Pegcetacoplan/TA\_TMA

Clinical Study No: Sobi.PEGCET-201

- g Laboratory tests: refer to Table 3. Blood and urine samples will be analyzed at a central unless a local laboratory facility is necessary, as defined in the laboratory manual. Urine samples will be analyzed by dipstick and microscopic analysis. The use of silica agents should be avoided in patients treated with pegcetacoplan.
- h Samples that are confirmed positive for anti-pegcetacoplan peptide or anti-PEG antibodies will be characterized with an antibody titer for that specific antibody. Any samples that are confirmed positive for anti-pegcetacoplan peptide antibody will be further characterized with a neutralizing antibody assay. If a clinic visit is on a dosing day, the sample should be taken predose but otherwise a sample is still required.
- i Pre-HSCT evaluations will be accepted as screening tests.
- k β-HCG for women of childbearing potential and FSH for postmenopausal women. For women of childbearing potential, a serum pregnancy test will be performed at screening. Urine pregnancy tests will be performed at all subsequent site visits. Patients with positive results will be excluded or discontinued from the study.
- m All AEs occurring upon receiving the first IMP dose up to 8 weeks after last IMP administration must be recorded in the eCRF. SAEs will be reported from signing of the ICF up to 8 weeks after last IMP administration. New SAEs occurring at any time after the 8-week AE follow-up period up to EOS should be reported only if considered causally related to previous exposure to the IMP by the investigator.
- o An EOT/ET visit will be performed 4 weeks after the last dose of pegcetacoplan. For patients who complete 12 weeks of treatment, the EOT visit will be at Week 16, and there will be further follow-up visits at Weeks 20 and 24. For patients who complete 16 weeks of treatment, the EOT visit will be at Week 20 and there will be a further follow-up visit at Week 24. The main analysis will be performed after all patients have completed their Week 24 visit.
- p Blood collection for safety laboratory tests at Day 1 can be omitted if screening samples were collected on Day -1.

Note: On dosing days, all blood samples will be collected predose. The date and time of the sample and the date and time of the previous dose of pegcetacoplan must be recorded in the eCRF.

Note: Unscheduled additional visits may be performed at the investigator's judgment. Any of the study procedures or other assessments may be performed at the unscheduled visit at the discretion of the investigator.

Confidential Page 89 of 89

	8.8.2, 8.8.3	Study endpoints updated	To reflect changes to the study endpoints in the protocol
	8.8.2, 8.8.3	Details have been added	To make content clearer and unambiguous
	8.9.1	Coding dictionary details added and new categories of TEAEs added	To provide more details on AEs
	8.9.1	Section updated	To align the AE section to another PEGCET study to align presentation of Aes.
	9	Administrative interim analysis added	To reflect changes in the protocol
	10	All deviations from protocol previously mentioned have been removed as now clearly stated in the protocol. Only TEAE of Special Interest item has been kept.	To reflect changes in the protocol
	13.1	Clinical response derivation updated	To reflect changes in the protocol
	13.2	Section added	To make content clearer and unambiguous
	13.3	Section renumbered	To reflect updates to SAP text due to Section 13.2 added.
3.0	NA	SAP reviewers were updated and co-author for PK section was added.	To reflect updates in the study team
	NA	The unit of platelet count has been updated from /mm³ to 10^9/L	To ensure consistency with SDTM datasets
	1	List of abbreviations updated	To reflect updates to SAP text
	2	Study protocol and eCRF version updated	To reflect latest study documents
	4.1, 4.2	Section updated	To reflect latest study documents

5	Section updated	To correct typographical issues
6.1, 6.2, 6.3	Section updated	To make content clearer and unambiguous
8.1	Section updated	To make content clearer and unambiguous
8.2	Section updated	To make content clearer and unambiguous and to update the derivation of baseline.
8.3	Section updated	To correct typographical issues and to update the derivation of baseline.
8.4	Section updated for procedure	To make content clearer and unambiguous
8.5	"Completion and reasons for premature discontinuation from treatment phase and from follow-up" has been updated to "completion and reasons for premature discontinuation from treatment and study"	To reflect changes in the eCRF as End of Study (EOS) form has been added
8.5	Enrollment by country is now tabulated and listed.	To provide further information.
8.6	Section updated	To correct typographical issues
8.7.1	Frequency of drinking alcohol/smoking were added back and age in categories was added too.	To provide further information on study population.
8.7.2	Section updated	To make content clearer and unambiguous
8.7.3	Section updated	To make content clearer and unambiguous
8.7.4	Section updated	To make content clearer and unambiguous
8.7.5	A new category for infusion- level and volume-level compliances has been added and details about calculation of compliance has been added.	To ensure clarity in the reporting of data related to study drug administration
8.8.1	Section updated	To make content clearer and unambiguous
8.8.2.2	List of prohibited medications updated.	To reflect latest study documents
	· · · · · · · · · · · · · · · · · · ·	· · · · · · · · · · · · · · · · · · ·

Page 5 of 39

8.8.2.	3 Section u	pdated	To correct typographical issues and hyperlink to the appropriate section.
8.8.2.4 Section updated		To correct typographical issues	
8.8.2.	5 Section u	pdated	To correct typographical issues and hyperlink to the appropriate section.
8.8.2. 8.8.2.	7 protocol with the first of th	pdated to clarify the wording. The event is ccurrence of response. In that no response at up to week 24, then were to ensored. But the mentioned above are its achieving response are not able to have sored events.	To make content clearer and unambiguous hyperlink to the appropriate section.
		rephrase the two sets ned or not sustained	
8.8.2. 8.8.2.	9 fact that r	pdated to clarify the eported TA-TMA s from Survival Status m	To make content clearer and unambiguous
8.8.2. 8.8.2.	9 date of the TMA) resclinical (Treported Survival Street death from considered patient considered this is considered that no real at the date of the considered that the date of the considered that no real the date of the considered that the considered t	date is defined as the le earliest clinical (TA-ponse. The loss of TA-TMA) response, the TA-TMA relapse as per Status eCRF form and many cause are led as events. So, a build have a clinical response and then this should be led as an event, and intradictory to the "patients who died leapse will be censored the of death". This has been removed	To make content clearer and unambiguous
8.8.2.	9 Section u	pdated	To hyperlink to the appropriate section.
8.8.2.	confidence proportion	pdated to have be interval for n of patients with TA- pse and not	To correct typographical issues

		responders	
8.8.2 8.8.2		Section updated	To hyperlink to the appropriate section.
8.8.3	3.1	Section updated	To make content clearer and unambiguous
8.8.3		Section updated by adding a restriction that subgroup analyses will only be presented if we have at least 3 patients in a subgroup category	To ensure that the presented subgroup analyses are meaningful

1. LIST OF ABBREVIATIONS

ADAs	Anti-drug antibodies
AE	Adverse Event
ATC	Anatomical Therapeutic Chemical
AUC _{0-taud1-d3}	Area under the concentration-time curve over the dosing interval on
AUC0-taud1-d3	days 1 to 3
AUC _{0-taud3-d5}	Area under the concentration-time curve over the dosing interval on
AUC0-taud3-d5	days 3 to 5
AUC _{0-taud5-d8}	Area under the concentration-time curve over the dosing interval on
AUC _{0-taud} 5-d8	
DATAD	days 5 to 8
BATAP	Bilirubin, Age, Thrombocytopenia, Anemia, Proteinuria
Bb	Activated factor B
BLQ	Below Limit of Quantification
C3	Complement component 3
C3a	Complement component 3a
C4a	Complement component 4a
C _{max}	Maximum observed serum concentration
CI	Confidence interval
CNS	Central Nervous System
COVID-19	Coronavirus disease 19
Ctrough	Observed serum concentration predose
CV	Coefficient of variation
DBL	Database lock
ECG	Electrocardiogram
eCRF	Electronic Case Report Form
EOT	End of Treatment
ET	Early Termination
	Larry Formination
GCV	Geometric coefficient of variation
GI	Gastrointestinal
GVHD	Graft-versus-host disease
Hb	Hemoglobin
HSCT	
	Hematopoietic stem cell transplantation
ICE	Intercurrent event
ICF	Informed Consent Form
IMP	
IMP	Investigational medicinal product
ITT	Intent-to-treat
LD H	Lactate dehydrogenase
LOQ	Limit of Quantification
MAGIC	Mount Sinai Acute Graft-versus-host disease International Consortium
MedDRA	Medical Dictionary for Regulatory Activities

Page 12 of 39

PD	Pharmacodynamic(s)
PEG	Polyethylene glycol
PK	Pharmacokinetic(s)
PRBC	Packed red blood cells
PRES	Posterior Reversible Encephalopathy Syndrome
PT	Preferred Term
QOL	Quality of life
rUPCR	Random urine protein/creatinine ratio
SAP	Statistical Analysis Plan
S.C.	Subcutaneous(ly)
sC5b-9	Terminal complement complex (soluble)
SD	Standard deviation
SOC	System Organ Class
SRC	Safety Review Committee
TA-TMA	Transplant-associated thrombotic microangiopathy
TBI	Total-body irradiation
TEAE	Treatment-emergent adverse event
TFLs	Tables, listings, and figures
T _{max}	Time to the maximum observed serum concentration
TOI	Trial Outcome Index
ULN	Upper limit of normal
VAS	Visual analogue scale
WHO-DD	World Health Organization-Drug Dictionary

2. INTRODUCTION

This Statistical Analysis Plan (SAP) covers the statistical analyses and reporting plans for the protocol Sobi.PEGCET-201 Version 3.0 dated 17 September 2024 and for the final electronic Case Report Form (eCRF) dated 21 September 2023.

3. STUDY OBJECTIVES

3.1 PRIMARY OBJECTIVES

The primary objective of this study is to evaluate the pharmacokinetics (PK), safety and tolerability of pegcetacoplan in patients with TA-TMA.

3.2 SECONDARY OBJECTIVES

The secondary objectives of this study are:

- To evaluate the pharmacodynamics (PD) of pegcetacoplan in patients with TA-TMA
- To evaluate the efficacy of pegcetacoplan in patients with TA-TMA

4. STUDY DESCRIPTION

4.1 STUDY DESIGN

This is a prospective, open-label, multicenter, single-arm, pilot study to evaluate the PK, PD, efficacy, and safety of pegcetacoplan in patients with TA-TMA after HSCT.

The study will enroll 12 patients with TA-TMA, who will receive treatment with open-label pegcetacoplan at the planned dose regimen presented in Section §4.2.

The planned study duration for each patient is up to 24 weeks. The study will consist of the following periods:

- Screening period (up to 2 weeks),
- Treatment period (up to 16 weeks) and
- Follow-up period (up to 12 weeks).

The main analysis will be performed after all enrolled patients have completed the follow-up period and performed the End of study visit at the Week 24 visit or the Early Termination visit in case of early discontinuation.

A Safety Review Committee (SRC) will assess the progress and cumulative PK, PD, safety and efficacy data of the study.

4.2 STUDY TREATMENT

All patients will receive

pegcetacoplan

(see Section §6.4.1 of the protocol).

At Week 12, if a clinical and/or TMA response according to the protocol definition is not reached, the investigator may decide according to his/her judgment to continue treatment for additional 4 weeks until a total of 16 weeks of treatment. If at Week 12 the patient has reached a partial clinical response, 4 additional weeks of pegcetacoplan every 3 days will be administered to complete 16 weeks of treatment.

At any time after the first 3 weeks of treatment, in the event of significant clinical worsening associated with active laboratory TMA (as defined in Section §6.1.2.1 of the protocol), the patient may be discontinued from study treatment and receive rescue therapy. In case of earlier clinical worsening, it is recommended to wait until at least 3 weeks of treatment are completed to allow pegcetacoplan to reach the target exposure and exert a clinical effect; however, if deemed by the investigator that the patient's safety is at risk, the patient can be discontinued from study treatment at any time. Discontinued patients will remain on study and will be followed for survival until the end of the study.

Any concomitant TA-TMA directed therapy will be prohibited for the entire treatment period, including plasma-exchange, defibrotide and any other complement inhibitor.

5. SAMPLE SIZE AND POWER CALCULATION

This is a pilot study, and the sample size is based on practical rather than statistical aspects.

A total of 12 patients will be included and treated in the study. With 12 patients included, it is estimated that 9 patients will complete at least 4 weeks of treatment, which is deemed sufficient to characterize the PK of pegcetacoplan in patients with TA-TMA to an appropriate precision. In addition, 12 patients will provide a 72% probability to observe a response rate of at least 8 responders of the 12 patients recruited (assuming the true response rate is 70%).

6. ANALYSIS ENDPOINTS

6.1 PRIMARY ENDPOINTS

The primary PK endpoints of this study are PK parameters for pegcetacoplan on Day 1, 3, and 5: Area under the concentration-time curve over the dosing interval on days 1 to 3 ($AUC_{0-taud1-d3}$), 3 to 5 ($AUC_{0-taud3-d5}$) and 5 to 8 ($AUC_{0-taud5-d8}$). Maximum observed serum concentration (C_{max}), Time to the maximum observed serum concentration (T_{max}) and Observed serum trough concentration pre-dose (T_{tough}) at all visits.

The primary safety endpoints are as follows:

- Occurrence of treatment-emergent adverse events (TEAEs)
- Changes from baseline in laboratory parameters and vital signs
- · Occurrence of clinically significant abnormal electrocardiogram (ECG) findings
- Presence of antibodies to polyethylene glycol (PEG) and pegcetacoplan throughout treatment and follow-up periods

6.2 SECONDARY ENDPOINTS

Secondary endpoints are as follows:

PD endpoints:

Protocol Sobi.PEGCET-201 Page 15 of 39

Absolute levels, change from baseline, and % change from baseline to Week 24 in biomarkers
of complement activation: terminal complement complex (soluble) (sC5b-9), complement
component 3a (C3a), complement component 3 (C3), activated factor B (Bb), complement
component 4a (C4a), functional assays for classical and alternative complement pathways.

• Clinical response at Week 24, defined as improvement in laboratory markers and improvement in clinical status as follows:

Improvement in laboratory markers:

- Lactate dehydrogenase (LDH) < 1.5 x upper limit of normal (ULN) and
- Platelet count ≥ 50*10^9/L (50 000/ mm³) without transfusion support during the prior 7 days.

AND in patients with signs or symptoms of organ dysfunction at baseline, in addition to the above laboratory markers, at least 1 of the following clinical criteria needs to be fulfilled, depending on the organ/system involved at baseline (without appearance of new signs or symptoms of organ dysfunction in other organs not present at baseline):

- Renal response requires > 40 % reduction in creatinine, or normalization of creatinine, or discontinuation of renal replacement therapy, or ≥ 50 % reduction from baseline in random urine protein/creatinine ratio (rUPCR)
- **Pulmonary response** requires extubation and discontinuation of positive pressure ventilation
- Gastrointestinal (GI) response applicable only to patients with biopsy-proven GI TA-TMA and requires improvement in GI function as determined by the Mount Sinai Acute Graft-versus-host disease International Consortium (MAGIC) criteria (no or intermittent nausea, vomiting or anorexia attributed to TA-TMA for upper GI; stool output/day for lower GI as follows: < 500 mL/day or < 3 episodes/day)
- **Neurological response** requires improvement in reversible neurological conditions (e.g., cessation of seizures or controlled under medication, resolution of mental alteration; residual radiologic signs are acceptable without clinical symptomatology), or stabilization of irreversible. neurological conditions (e.g., stability of neurological deficits following stroke without further deterioration or subsequent strokes)
- Freedom from transfusion requires absence of platelet or packed red blood cells (PRBC) transfusions attributed to TA-TMA during the prior 7 days (only applicable if patient was undergoing platelet or PRBC transfusion at baseline)
- Cardiovascular response requires resolution of pulmonary hypertension (may receive antipulmonary hypertension medications if still on maintenance therapy), or hypertension control on no more than 2 medications excluding diuretics (applicable only to patients with severe hypertension at baseline)
- **Serositis response** requires no evidence of clinically significant pericardial or pleural effusion requiring surgical therapy (e.g., pericardiocentesis/thoracocentesis)

Patients meeting intercurrent events, including use of prohibited medication or study withdrawal before Week 24 will be considered as failures/non-responders.

The exact rules to be used for the derivation of the clinical response are described in Appendix I (Section 13.1).

- TMA response at Week 24, defined as improvement of laboratory markers as follows:
 - LDH < 1.5 x ULN **and**
 - Platelet count ≥ 50*10^9/L (50 000/ mm³) without transfusion support during the prior 7 days and
 - ≥ 50 % reduction from baseline in rUPCR.
- Overall survival at Day 100 from date of TA-TMA diagnosis
- Overall survival at Week 24 from treatment start

- · Time to clinical response
- Time to TMA response
- Duration of clinical response
- Duration of TMA response
- TA-TMA relapse at Week 24
- Clinical response at Week 12
- TMA response at Week 12

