# 6.3 Selection of study population

#### 6.3.1 Inclusion criteria

A patient must fulfill the following criteria in order to be included in the study:

- 1. Male and female patients aged  $\geq$  18 years at the time of ICF signature.
- 2. Received allogeneic HSCT from a related or unrelated, human leukocyte antigen-matched or mismatched donor. Patients having received any of the following stem cell sources are eligible: granulocyte colony stimulating factor mobilized peripheral blood stem cells, bone marrow, umbilical cord blood.
- 3. Diagnosis of TA-TMA established as per the laboratory markers below, indicating TMA:
  - a. De novo or progressing thrombocytopenia (platelet count  $< 50 \times 10^9/L$  or > 50 % decrease in platelet count from the highest value achieved after transplantation). AND
  - b. Elevated LDH (> 1.5 x ULN).

AND at least 2 additional laboratory/clinical criteria among the following:

- c. Presence of schistocytes on the peripheral blood smear (≥ 2 per hpf) or histologic evidence of microangiopathy in any biopsied organ. OR
- d. De novo anemia (hemoglobin < LLN or anemia requiring PRBC transfusion support as per local institutional standard). OR
- e. Proteinuria (random urinalysis protein concentration  $\geq 30$  mg). OR

Confidential Page 35 of 89

- Clinical Study No: Sobi.PEGCET-201
- f. Elevated plasma concentration of sC5b-9 above ULN. OR
- g. Arterial hypertension, defined by systolic BP ≥ 140 mmHg and/or diastolic BP ≥ 90 mmHg.
- 4. Have a diagnosis of TA-TMA that persists despite initial management of any triggering condition.
- 5. Have a rUPCR  $\geq 1$  mg/mg.
- 6. Women of childbearing potential, defined as any women who have experienced menarche and who are NOT permanently sterile or postmenopausal, must have a negative serum pregnancy test at screening and agree to use protocol-defined methods of contraception for the duration of the study and 8 weeks after their last dose of IMP.

Note: Postmenopausal is defined as having had 12 consecutive months with no menses without an alternative medical cause.

- 7. Men must agree to the following for the duration of the study and 8 weeks after their last dose of IMP:
  - a. Avoid fathering a child.
  - b. Use protocol-defined methods of contraception.
  - c. Refrain from donating sperm.
- 8. Patient and/or legally authorized representative must be capable of giving signed informed consent, which includes compliance with the requirements and restrictions listed in the ICF.

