#### 6.5.7.3 Overall survival, time to response, duration of response, TA-TMA relapse

Overall survival will be assessed at Day 100 from the day of TA-TMA diagnosis and at Week 24 from treatment start. The day of TA-TMA diagnosis will be defined as the earliest date when all required laboratory criteria outlined in Inclusion Criterion #3 are met. Date of death and reason for death will be collected (whether related to TA-TMA or not).

Time to clinical/TMA response will be measured from the time of first IMP dose to the first documentation of attainment of a clinical or of a TMA response as defined in Section 5.2.1. Duration of clinical and of TMA response will be measured from the first documentation of attainment of a response until TA-TMA relapse.

Confidential Page 58 of 89

[figure not shown]
Pegcetacoplan/TA TMA

Clinical Study No: Sobi.PEGCET-201

TA-TMA relapse will be defined as reappearance of all laboratory markers as outlined in Inclusion Criterion #3 in a patient who has reached a clinical response.

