8.7.2 MEDICAL HISTORY AND CURRENT MEDICAL CONDITIONS

Medical history (conditions that ended before the date of enrollment) and current medical conditions (those that started before and were ongoing at the date of enrollment) will be coded using the Medical Dictionary for Regulatory Activities (MedDRA) version current at the time of DBL and tabulated by System Organ Class (SOC) and Preferred Term (PT).

Baseline TA-TMA data will be summarized using the following variables:

- The platelet value at the diagnosis (10^9/L),
- The highest platelet value achieved after transplant (10^9/L),
- The LDH value at diagnosis (U/L),
- Diagnosis of TA-TMA established as per laboratory/clinical markers indicating TMA.
 - o Presence of schistocytes in the peripheral blood smear (yes or no),
 - Absolute number of schistocytes per high power field in the peripheral blood smear (per hpf),
 - o Was any biopsy performed to confirm the histologic diagnosis of TA-TMA (yes or no),
 - If yes, sample location,
 - o De novo anemia at diagnosis (yes or no)
 - The most recent pre-transfusion hemoglobin (Hb) level at diagnosis (g/dL),
 - Proteinuria at diagnosis (yes or no),

Page 21 of 39

- The most recent rUPCR value at diagnosis (mg/mg).
- The most recent proteinuria value at diagnosis (mg/dL),
- Elevated plasma concentration of Sc5b-9 above ULN (yes or no),
 - Sc5b-9 level at diagnosis (ng/mL),
- Arterial hypertension defined by systolic blood pressure (BP) ≥ 140 mmHg and/or diastolic BP ≥ 90 mmHg (yes or no),
 - The pre-antihypertensive therapy systolic blood pressure (mmHg),
 - The pre-antihypertensive therapy diastolic blood pressure (mmHg),
 - Patients taking any antihypertension medication (yes or no),
 - Number of ongoing medications, excluding diuretics,
 - 0 medication,
 - ≤ 2 medications,
 - > 2 medications,
- o Time between HSCT and TA-TMA diagnosis (days),
- o Time between TA-TMA diagnosis and study enrollment (days).
- o TA-TMA persisting despite initial management of any triggering condition (yes or no),
- o Any sign/symptom of kidney dysfunction (yes or no),
 - The most recent serum creatinine value (mg/dL),
 - The last serum creatinine value pre-transplant (mg/dL),
 - Patients requiring renal replacement therapy (yes or no),
- Any sign/symptom of lungs dysfunction (yes or no),
 - The lowest oxygen level in the blood (%),
 - Patients receiving noninvasive positive pressure ventilation (yes or no),

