13.2 APPENDIX II. DERIVATION RULES FOR TMA RESPONSE

[figure not shown]
eCRF forms: Platelet or PRBC Transfusion form, Central laboratory sampling form.

TMA response is defined as improvement in laboratory markers as follows:

IF [(LDH < 1.5 x ULN) AND (Platelet count ≥ 50*10^9/L (50 000/mm³)) AND ≥ 50% reduction from baseline in rUPCR AND

((Any blood transfusions performed=No) **OR**((Any blood transfusions performed=Yes) **AND** (Type of blood transfusion=PRBC **OR**Type of blood transfusion=Platelet) **AND** (Date of blood sample taken> Date of last platelet transfusion + 7 days)))]

THEN TMA response =1 **ELSE** TMA response=0

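### Patients enrolled on the relative platelet-fall branch can already meet the platelet limb of response on Day 1, so the plan should count them and add a sensitivity row

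*SAP*

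**What the plan says.** **Entry.** Protocol 6.3.1, criterion 3a, is met in either of two ways: an absolute count below 50 x 10^9/L, or a more than 50% "decrease in platelet count from the highest value achieved after transplantation". The second way carries no upper limit on the count. Criterion 3b must also hold: "Elevated LDH (> 1.5 x ULN".

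**Response.** SAP 6.2 asks for "Lactate dehydrogenase (LDH) < 1.5 x upper limit of normal (ULN) and" together with "Platelet count ≥ 50*10^9/L (50 000/ mm³) without transfusion support during the prior 7 days". Both stand under the label of improvement in laboratory markers. TMA response carries the same label ("TMA response at Week 24, defined as improvement of laboratory markers as follows") and adds a fall of at least 50% from baseline in rUPCR.

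**Code.** SAP Appendix II reads "IF [(LDH < 1.5 x ULN) AND (Platelet count ≥ 50*10^9/L (50 000/mm³)) AND ≥ 50% reduction from baseline in rUPCR AND", followed by the transfusion condition. Appendix I uses the same LDH and platelet thresholds for clinical response. Neither appendix refers to the baseline platelet count or to the post-transplant peak.

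**Data.** The peak is collected. SAP 8.7.2 summarises "The highest platelet value achieved after transplant (10^9/L") among the baseline TA-TMA data, but the response derivation does not use it.

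**The concern.** The other two laboratory components are tied to the patient's starting state. LDH must move from above to below the cut-off used for entry, and rUPCR is judged against baseline. The platelet limb has no such tie. A patient whose count fell from 200 to 80 is eligible on the second branch of 3a. Without a recent platelet transfusion, that patient meets the platelet limb before the first dose has had any effect, and still satisfies 3a at a visit scored as platelet-responding.

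For such a patient, the laboratory step of clinical response depends on LDH alone. At stake is how far a response rate from a 12-patient single-arm study can be read as platelet recovery. Time to response is also exposed, because one of its two analyses in SAP 8.8.2.6 counts the first response at any visit, sustained or not.

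**Working it through.** **1. The plan's own figure.** Protocol 8.1 and SAP 5 give a 72% probability of at least 8 responders among 12 at a true rate of 70%. The exact binomial tail is P(X >= 8 | n = 12, p = 0.70) = 0.7237, so the figure is reproduced. Nothing below disputes it.

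**2. Where entry and response overlap.** Let P be the post-transplant peak (10^9/L). The relative branch needs a count < P/2 and the response limb needs a count >= 50. Both hold when 50 <= count < P/2, which is possible only if P > 100.

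| Peak P | Counts meeting both |
|---|---|
| 100 or less | none |
| 120 | 50 to < 60 |
| 150 | 50 to < 75 |
| 200 | 50 to < 100 |
| 300 | 50 to < 150 |

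Example: with P = 200 and a count of 80, the fall is (200 - 80)/200 = 60%, so 3a is met, and 80 >= 50, so the limb is met. If the count then drops to 50 (75% below the peak), the limb is still met. Meeting the whole limb also requires that the last platelet transfusion was more than 7 days earlier.

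**3. A no-effect case.** The inputs in this step are assumptions; the documents give none of them. True count 80, peak 200, constant LDH of L x ULN, lognormal visit noise with log-SD s of 0.15 or 0.25, and independence across markers and visits.

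- Platelet limb: Φ(ln(80/50)/s) = 99.9% (s = 0.15) or 97.0% (s = 0.25).
- LDH limb: Φ(ln(1.5/L)/s).
- Laboratory rule at one visit: the product of these two.
- At least once in 12 visits: 1 - (1 - product)^12.
- Requiring also that the count is not more than 50% below the peak (here >= 100): replace the platelet term by Φ(ln(80/100)/s) = 6.8% or 18.6%.
- rUPCR limb of TMA response, with no true change and the same noise at baseline and visit: Φ(ln(0.5)/(s√2)) = 0.05% or 2.5%.

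| L | s | LDH + platelets, per visit | Any of 12 visits | Per visit if 3a must have resolved | Full TMA response, per visit |
|---|---|---|---|---|---|
| 1.6 | 0.15 | 33% | 99% | 2.3% | 0.02% |
| 1.6 | 0.25 | 39% | > 99% | 7.4% | 1.0% |
| 1.8 | 0.15 | 11% | 76% | 0.8% | 0.01% |
| 1.8 | 0.25 | 23% | 95% | 4.3% | 0.6% |
| 2.2 | 0.15 | 0.5% | 6% | < 0.1% | < 0.01% |
| 2.2 | 0.25 | 6% | 53% | 1.2% | 0.2% |

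For comparison, a patient entering at 30 has a platelet term of Φ(ln(30/50)/s) = 0.03% or 2.1%. The laboratory rule is then met at under 1% of visits for every L above.

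**4. What these figures cover.** The fourth and fifth columns, like the third, concern only the LDH and platelet components. They are not rates for an endpoint. Every enrolled patient has rUPCR >= 1 mg/mg (criterion 5), which Protocol 6.5.1 counts as kidney injury, and the last step of Appendix I requires at least one organ response. Clinical response therefore always needs more than the laboratory rule. The false rate for full clinical response was not computed.

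**The case against.** **Against the point.** An absolute, transfusion-free platelet threshold is a legitimate choice and is the protocol's own definition (Protocol 5.2.1), not something the SAP introduced. Response endpoints are secondary and descriptive in a pilot whose primary endpoints are PK and safety. Counts are summarised by visit with change from baseline (SAP 8.9.2) and all data are listed (SAP 8.1), so with 12 patients any such case can be found by hand. All of this stands. It argues against replacing the endpoint, but not against counting the affected patients: no planned table links the baseline count to response.

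**Stronger readings that the documents do not support.**

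- *That response rates are inflated by 11 to 39%, or nearly always over 12 visits.* Those figures belong to the laboratory components and depend on LDH sitting just above the cut-off. At 2.2 x ULN they fall to 0.5 to 6% per visit. The rUPCR requirement brings TMA response to about 1% or less per visit. This does not bound clinical response, because some coded organ criteria can be met without improvement. For example, hypoxemia alone counts as lung injury in Protocol 6.5.1, while Appendix I scores pulmonary response as absence of ventilation.
- *That relapse cannot be read for these patients.* Protocol 6.5.7.3 says "TA-TMA relapse will be defined as reappearance of all laboratory markers as outlined in Inclusion Criterion #3", and that criterion requires both the platelet condition and LDH above 1.5 x ULN. A responder has LDH below the cut-off, so the set is no longer met and can be met again when LDH rises.
- *That the main definition should change.* SAP 10 describes recruitment in the past tense and the study is open-label, so a new main endpoint would be a late redefinition. A rule applied only to patients with baseline counts of 50 or more would also be discontinuous. With a peak of 300, a baseline of 49 would need 50 but a baseline of 51 would need 150. And a patient entering at 30 with a peak of 200 could still respond at 60, which is 70% below the peak.

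**Conclusion.** The point holds in a limited form, as a cheap improvement. A patient enrolled on the relative branch of 3a, with a baseline count of at least 50 x 10^9/L, a peak above 100 and no recent platelet transfusion, meets the platelet limb of both response endpoints on Day 1. For that patient, laboratory improvement needs no platelet improvement. This follows from the wording and the code alone, and nothing elsewhere in the documents corrects it.

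The effect on the endpoints is smaller than the laboratory-rule figures suggest: about 1% or less per visit for TMA response under the assumed no-effect case, and not estimated for clinical response. The number of affected patients is not given and may be zero. Any patient whose classification did depend on this would move the rate by 1/12 = 8.3 points.

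**What to change.** Keep the protocol definition as the main analysis. Then:

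1. In SAP 8.8.2.2 and 8.8.2.3, tabulate how many patients meet the platelet limb on Day 1, split by baseline count < 50 versus >= 50 x 10^9/L.
2. Add one sensitivity row, specified before database lock, for clinical and TMA response at Weeks 12 and 24 and for time to response (SAP 8.8.2.6 and 8.8.2.7). In it, require for all patients that criterion 3a is no longer met: a count of at least 50 that is also not more than 50% below the highest post-transplant value on the baseline TA-TMA form. Applying it to everyone avoids the jump at a baseline of 50 and covers low-entry patients.
3. Declare the addition in SAP 10.

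The cost is a few lines of code and one extra row, with no new data collection. The extra row may show a lower response rate than the main one. It cannot show a higher one, because it only adds a condition.
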